#### 1. **Glossary of Abbreviations**

Abbreviation	Description
ACT	Asthma Control Test
AD	Atopic Dermatitis
CCI	CCI
AE	Adverse Event
AESI	Adverse Event of Special Interest
ANCOVA	Analysis of Covariance
CCI	
ATC	Anatomical Therapeutic Chemical
CCI	
ВМІ	Body Mass Index
CI	Confidence Interval
СМН	Cochran-Mantel-Haenszel
COVID-19	Coronavirus Disease-19
CRF	Case Report Form
CRO	Clinical Research Organization
CV	Coefficient of Variation
DCS	Dual-chamber, single-use Syringe
CCI	
ECG	Electrocardiogram
ELISA	Enzyme-linked Immunosorbent Screening Assay
GMC	Geometric mean concentrations
GMT	Geometric mean of titers
IAC	Independent Adjudication Committee
ICF	Informed Consent Form
ICH	International Conference on Harmonization
IDMC	Independent Data Monitoring Committee
CCI	
IgG	Immunoglobulin G

Abbreviation	Description
IMP	Investigational Medicine Product
IRR	Injection-related Reaction
IRT	Interactive Response Technology
ITT	Intent-to-treat
LLOQ	Lower Limit of Quantification
LTE	Long-term Extension
MAR	Missing at Random
Max	Maximum
MedDRA	Medical Dictionary for Regulatory Activities
MenC	Meningococcal Serogroup C
МІ	Multiple Imputation
Min	Minimum
mITT	modified Intent-to-treat
MMRM	Mixed-effect Model for Repeated Measures
MNAR	Missing Not at Random
N/A	Not Applicable
NA	Not Applicable
NCA	Non-compartmental Analysis
ОС	Observed Case
PE	Physical Examination
PEF	Peak Expiratory Flow
PK	Pharmacokinetics
PKAP	Pharmacokinetic Analysis Population
CCI	
PT	Preferred Term
Q4W	Every 4 Weeks
QC	Quality Control
SAE	Serious Adverse Event
SAF	Safety Population
SAP	Statistical Analysis Plan
SBA	Serum Bactericidal Assay

Abbreviation	Description
SD	Standard Deviation
CCI	
SE	Standard Error
soc	System Organ Class
SOP	Standard Operating Procedure
ТВ	Tuberculosis
TCI	Topical Calcineurin Inhibitor
TCS	Topical Corticosteroid
TEAE	Treatment Emergent Adverse Event
TFL	Table, Figure and Figure
ULOQ	Upper Limit of Quantification
WHO DD	World Health Organization's Drug Dictionary
WOCBP	Women of Childbearing Potential

# 2. Purpose

The purpose of this statistical analysis plan (SAP) is to ensure that the data listings, summary tables and figures which will be produced, and the statistical methodologies that will be used, are complete and appropriate to allow valid conclusions regarding the study objectives.

# 2.1. Responsibilities

will perform the statistical analyses and are responsible for the production and quality control of all tables, figures and listings. Descriptive summary will be provided for pharmacokinetics parameters. The derivation of Pharmacokinetics parameters and the statistical modelling will be specified in a separate Modeling Analysis Plan and PK Analysis Plan, respectively.

# 3. Study Objectives

## 3.1. Primary Objective

The primary objective is to assess the effect of nemolizumab (CD14152) on humoral immune responses to tetanus and meningococcal vaccination in adult and adolescent subjects with moderate-to-severe atopic dermatitis (AD).

The main estimand for primary objective is listed as below:

Primary	The proportion of subjects with a positive serum IgG response to tetanus toxoid at	
Endpoint	Week 16 (4 weeks post-vaccination) defined as:	
	≥ 4-fold increase in anti-tetanus IgG concentrations from baseline in subjects with pre-vaccination anti-tetanus IgG concentrations ≥ 0.1 IU/mL	
	OR	
	≥ 0.2 IU/mL anti-tetanus IgG concentrations in subjects with pre-vaccination anti-tetanus IgG concentrations < 0.1 IU/mL	
Population	Of all defined by the study inclusion / exclusion criteria, the analysis population will include all randomized subjects who received at least one dose of study drug and vaccine injection, have an evaluable vaccine response and did not receive any systemic rescue therapy prior to the post-vaccination vaccine response assessment (mITT population).	
Primary endpoint will be analyzed by the Cochran-Mantel-Haenszel (CMH) esti of the risk difference and corresponding 2-sided 90% CI, adjusted for randomization stratum baseline CCI using weight average of stratum-specific proportion.		
Intercurrent Event	None	

## 3.2. Secondary Objective(s)

The secondary objectives are to assess the safety and efficacy of nemolizumab (CD14152) after a 16-week treatment period in adult and adolescent subjects with moderate-to-severe AD.

#### 3.3. Brief Description

This is a randomized, double-blind, placebo-controlled, multi-center, parallel-group study in adult and adolescent subjects (≥ 12 to 54 years) with moderate-to-severe AD. Eligible subjects must have a documented history of inadequate response to topical AD medication(s).

Approximately 245 subjects will be randomized 1:1 to receive either 30 mg nemolizumab (with a 60 mg loading dose) or placebo, stratified by baseline disease severity

The study consists of a 2- to 4-week screening period, a 16-week treatment period, and an 8-week follow-up period (12 weeks after the last study drug injection).

The screening period will evaluate subject eligibility. Subjects will apply a moisturizer at least once daily, beginning at screening. Subjects using a stable regimen of low- or medium-potency topical corticosteroid (TCS) with or without topical calcineurin inhibitor (TCI) at the screening visit (ie, ≥ 14 days prior to the baseline visit) should continue their therapy regimen. Subjects not using a stable regimen of TCS with or

without TCI at the screening visit should not use these topical therapies during the study unless required as rescue therapy.

At the baseline visit, subjects will receive a loading dose of nemolizumab (60 mg) or placebo via 2 subcutaneous injections. Nemolizumab (30 mg) or placebo will then be administered via a single subcutaneous injection every 4 weeks (Q4W) at Week 4, 8, and 12. At the Week 12 visit, subjects will also receive single doses of tetanus toxoid, reduced diphtheria toxoid, and acellular pertussis (PPD and quadrivalent meningococcal conjugate PPD vaccines. Clinical assessments will occur according to the schedule of assessments. Refer to Figure 1 for an overview of the study design.

Subjects will continue to apply a moisturizer at least once daily throughout the study. Subjects using background topical therapy (TCS with or without TCI) from the screening visit will continue use in the treatment period, which should be adjusted according to the disease activity and tolerability, based on investigator clinical judgment. (Subjects not using background topical therapy from the screening visit should not apply background topical therapy in the study.) If deemed to be medically necessary by the investigator (eg, to control intolerable AD signs/symptoms), topical and/or phototherapy rescue therapies can be prescribed to any subject at any time during the study, except during the screening period.

Subjects who complete the Week 16 treatment period may be eligible to enroll into a long-term extension (LTE) study (Protocol 118163). The follow-up visit is not required for subjects who participate in the LTE study.

Subjects who decline or are not eligible to enter into the LTE study will complete a follow-up visit at Week 24 (12 weeks after their last study drug injection).

Subjects who discontinue the study prematurely should complete an early termination visit and a follow-up visit 12 weeks after their last study drug injection.

An independent data monitoring committee (IDMC) will review and monitor subject safety throughout the study, and an independent adjudication committee (IAC) will review all asthma-related adverse events (AEs).

An overview of the study design is present in the Figure 1.

Figure 1. Study Design

## 3.4. Subject Selection

Subjects will be selected based on the inclusion and exclusion criteria in Protocol Sections 8.1 and 8.2.

# 3.5. Determination of Sample Size

Approximately 245 subjects will be randomized (123 per arm) to show that the 90% confidence interval of the proportion difference between treatment groups will exclude a difference of more than 10%.

## 3.6. Treatment Assignment & Blinding

At the baseline visit, a unique randomization number will be assigned to an eligible subject via interactive response technology (IRT). Subjects will be randomized in a 1:1 ratio to receive either nemolizumab or placebo. The randomization scheme will be stratified by baseline disease severity to ensure appropriate distribution of assignment to the 2 treatment groups.

All attempts will be made to keep the study center staff and subjects blinded throughout the study. Members of the study center staff, including those responsible for dual-chamber, single-use syringe [DCS] preparation, will not have access to the randomized treatment assignment.

To ensure double-blind administration of study drug, the study center pharmacist(s) or other qualified personnel will prepare all nemolizumab or placebo treatments, according to the current version of the pharmacy manual, the instructions for use, and assigned DCS provided by the IRT system.

As there may be detectable differences between nemolizumab and placebo during the reconstitution

This document is confidential.

SAP Version: 5.0, 15Feb2024

Controlled Document ID: 3903A.01, Effective Date 29-Oct-2018

Filing requirements: TMF

process, the DCS is delivered for injection after the reconstitution is complete. The pharmacist (or other qualified personnel) preparing study medication should not be involved with any study assessments and should not discuss any aspects of study drug reconstitution with the subject/caregiver or study staff involved in subject interviews or study assessments.

To maintain the integrity of the study blinding, the bioanalytical laboratory staff who process/analyze the and the central laboratory staff who will analyze sample for vaccines response (immunogenicity) will not provide any information to sponsor, clinical research organization (CRO), or investigational study center personnel directly involved with the ongoing conduct of the study that may lead to unblinding during the ongoing study.

Unblinding of a subject's individual treatment code should occur only in case of a medical emergency or in the event of a serious medical condition that necessitates identification of the study drug for the welfare of that subject, as judged by the investigator. The emergency unblinding process utilizes IRT to allow the investigator to have unrestricted, immediate, and direct access to the subject's individual study treatment. When possible (ie, when the health of the subject is not immediately at risk), the investigator or sub-investigator is encouraged to consult with the medical monitor and the sponsor before breaking the blind.

When the blinding code is broken, the reason must be fully documented. If the code is broken by the investigator, the subject must be withdrawn from the study and must also be appropriately followed for a minimum of 12 weeks after the last dose of study drug.

The reporting requirements for unblinding are the same for reporting a serious adverse event (SAE).

The randomization code will remain blinded to all study sites and study team members until completion of the study and after the study database has been locked. Although initial treatment period results will be analyzed after all subjects have either completed the Week 16 visit, or have withdrawn or been discontinued from the study before Week 16, personnel from sponsor, CRO, and investigational sites directly involved with the ongoing conduct of the study will not have access to any information that may lead to unblinding for the ongoing maintenance evaluation.

The IDMC will review data at periodic intervals throughout the study as defined in the IDMC charter. The IDMC charter will specify the procedures for unblinding to ensure that treatment assignment remains undisclosed to all individuals involved in the direct execution and management of the study until the final database is locked.

## 3.7. Administration of Study Medication

At the baseline visit, subjects will receive a loading dose of nemolizumab (60 mg) or placebo via 2 subcutaneous injections. Nemolizumab (30 mg) or placebo will then be administered via a single subcutaneous injection every 4 weeks (Q4W) at Week 4, 8, and 12. At the Week 12 visit, Tdap and MCV4 vaccines will be administered separately each as a 0.5 mL intramuscular injection.

# 3.8. Study Procedures and Flowchart

Provision of a written, signed informed consent form (ICF) is required before any study-related procedures are performed.

The planned study assessments are in **Table 1**. At each visit, assessments/procedures should be performed in the following order:

This document is confidential.

SAP Version: 5.0, 15Feb2024

Controlled Document ID: 3903A.01, Effective Date 29-Oct-2018

Filing requirements: TMF

# 4. Endpoints

## 4.1. Primary Vaccine Response Endpoint

The primary endpoint of this study is the proportion of subjects with a positive serum immunoglobulin G (IgG) response to tetanus toxoid at Week 16 (4 weeks post-vaccination) defined as:

- ≥ 4-fold increase in anti-tetanus IgG concentrations from baseline in subjects with pre-vaccination anti-tetanus IgG concentrations ≥ 0.1 IU/mL, OR
- ≥ 0.2 IU/mL anti-tetanus IgG concentrations in subjects with pre-vaccination anti-tetanus IgG concentrations < 0.1 IU/mL

# 4.2. Secondary Endpoints

# 4.2.1. Secondary Vaccine Response Endpoints

The secondary vaccine response endpoints are as follows:

- Proportion of subjects with a positive serum IgG response to tetanus toxoid at Week 16 defined as:
  - ≥ 2-fold increase in anti-tetanus IgG concentrations from baseline in subjects with prevaccination anti-tetanus IgG concentrations ≥ 0.1 IU/mL, OR
  - ≥ 0.2 IU/mL anti-tetanus IgG concentrations in subjects with pre-vaccination anti-tetanus IgG concentrations < 0.1 IU/mL

- Proportion of subjects with serum anti-tetanus IgG concentrations of ≥ 0.1 IU/mL at Week 16
- Proportion of subjects with serum anti-tetanus IgG concentrations of ≥ 1.0 IU/mL at Week 16
- Proportion of subjects with a positive serum bactericidal antibody response to meningococcal serogroup C polysaccharide at Week 16 (4 weeks post-vaccination) defined as ≥ 4-fold increase in serum bactericidal assay (SBA) reciprocal titer from baseline
- Proportion of subjects with a positive serum bactericidal antibody response to meningococcal serogroup C polysaccharide at Week 16 defined as SBA reciprocal titer ≥ 8

[figure not shown]

# 4.2.3. Safety Endpoints

The safety endpoint of this study is as follows:

- Incidence and severity of AEs, including AEs of special interest (AESI) [defined in protocol Section 13.1.1], treatment-emergent AE (TEAE), and SAE.
- Clinical laboratory tests
- Physical examination and vital signs
- Respiratory examination and assessments (ie, asthma control test [ACT], peak expiratory flow [PEF])
- 12-lead electrocardiogram (ECG)

This document is confidential.

SAP Version: 5.0, 15Feb2024

Controlled Document ID: 3903A.01, Effective Date 29-Oct-2018

Filing requirements: TMF

Statistical Analysis Plan
Sponsor: Galderma S.A./Galderma R&D, LLC; Protocol No.: RD.06.SPR.118380 V4.0, 06Jul2022

# 5. Analysis Population

## 5.1. Screened Population

The Screened population comprises all subjects who signed the informed consent. This population includes screen failures, and randomized subjects. For clarity, screen failed subjects are defined as those subjects who fail to meet inclusion criteria or meet exclusion criteria and discontinued the study prior to randomization. Subjects that are re-screened will only be counted once, under the subject ID assigned for the repeat screening.

#### 5.2. Safety Population (SAF)

The SAF will consist of all randomized subjects who received at least one administration of study drug. The treatment group assignment in this population will be defined by the treatment actually received. This population will be used for all the analyses of safety endpoints.

#### 5.3. Intent-to-Treat Population (ITT)

The ITT population will consist of all randomized subjects. The ITT population will be the primary population for efficacy analyses. All analyses under the ITT population will be analyzed under the treatment group as randomized.

## 5.4. Modified Intent-to-Treat Population (mITT)

The mITT population will consist of all randomized subjects who received at least one dose of study drug and vaccine injection, have an evaluable vaccine response and did not receive any systemic rescue therapy prior to the post-vaccination vaccine response assessment.

An evaluable vaccine response is defined as measured responses to the tetanus toxoid vaccine, i.e. an evaluable serum IgG response to tetanus toxoid as per the protocol section 16.4.1. The mITT will be the primary population for vaccine response. All analyses under the mITT will be analyzed under the treatment group actually received.

## 5.5. Pharmacokinetic Analysis Population (PKAP)

The PK analysis population (PKAP) will consist of all subjects included in the SAF, with at least one measurable post-baseline PK concentration assessment. Similar to SAF, the treatment group assignment in this population will be defined by the treatment actually received. This population will be used for the analyses of PK.

# 6. General Aspects for Statistical Analysis

#### 6.1. General Methods

The statistical evaluation will be performed using SAS® software version 9.4 or higher (SAS Institute, Cary, NC). All data will be listed, and summary tables will be provided. Summary statistics will be presented by treatment group. Summaries will be presented for each treatment and overall for Demographic, Other Baseline Characteristics and Medication. For all other analyses, summaries will be presented for each treatment.

Continuous variables will be summarized using the number of observations (n), mean, standard deviation (SD), median, minimum, and maximum by treatment group. Categorical variables will be summarized using number of observations (n), frequency and percentages of subjects for each category by treatment group.

All statistical tests on the vaccine response endpoints will be conducted at the 2-sided 10% level and the 90% CI will be estimated. For all other endpoints, the statistical tests will be conducted at the 2-sided 5% level and the 95% CI will be estimated.

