16 STATISTICAL ANALYSIS

A statistical analysis plan (SAP) will be created and finalized before database lock. This document will provide details regarding the definition of analysis variables and analysis methodology to address all study objectives. The SAP will contain further detailed and technical descriptions of specific data conventions, calculations and of statistical procedures for executing the analyses that are specified in this protocol. Any changes made to the analysis after finalization of the SAP (ie, post-database lock) will be discussed and documented in the clinical study report.

The statistical evaluation will be performed using SAS® software version 9.4 or higher (SAS Institute, Cary, NC). All data will be listed, and summary tables will be provided. Summary statistics will be presented by treatment group. For continuous variables, data will be summarized with the number of subjects (N), mean, standard deviation, median, minimum, and maximum by treatment group. For categorical variables, data will be tabulated with the number and proportion of subjects for each category by treatment group.

Unless otherwise stated, the baseline value for any variable will be the last non-missing value taken prior to the receipt of study treatment at the Baseline visit (Day 1).

Unless otherwise stated, all statistical tests other than the primary vaccine response endpoint will be 2-sided and conducted at the 5% level. All presented confidence intervals will be 2-sided 95% confidence intervals.

A full discussion of inclusion/exclusion of subjects into the analysis populations described here will be provided close to database lock, including any decisions on data handling and other topics, and will be documented in the Blind Data Review Meeting (BDRM) Plan and subsequently in the BDRM Report. No Per-Protocol population is included in this study.

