16.4.2 Analysis of Primary Vaccine Response Endpoint

The estimate of the corresponding proportion for the endpoint will be adjusted for the randomization strata baseline **CCI** using the Cochran-Mantel-Haenszel (CMH) estimate of the risk difference and corresponding 2-sided 90% CI. This primary analysis will be conducted on the mITT population.

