# 8. Vaccine Response Analysis

## 8.1. Primary Vaccine Response Endpoint and Analysis

# **8.1.1.** Primary Analysis of Primary Endpoint

The primary endpoint of this study is the proportion of subjects with a positive serum IgG response to tetanus toxoid at Week 16 (4 weeks post-vaccination), defined as:

- ≥ 4-fold increase in anti-tetanus IgG concentrations from baseline in subjects with pre-vaccination anti-tetanus IgG concentrations ≥ 0.1 IU/mL, OR
- ≥ 0.2 IU/mL anti-tetanus IgG concentrations in subjects with pre-vaccination anti-tetanus IgG concentrations < 0.1 IU/mL

Anti-tetanus IgG concentrations and the ratio from baseline will be summarized by treatment group and by visit using descriptive statistics.

The analysis for primary endpoint will be using the Cochran-Mantel-Haenszel (CMH) estimate of the risk difference and corresponding 2-sided 90% CI. It will be adjusted for the randomization stratum baseline using weighted average of stratum-specific proportion using CMH.

The example SAS code for CMH model is included in Section 20.1. The primary analysis will be conducted on the mITT population.

Subjects in receipt of systemic rescue medication will not be vaccinated. As the primary analysis will be conducted on the mITT, no imputation is required.

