#### **8.1.2.** Sensitivity Analysis of Primary Endpoint

Three sensitivity analyses will be performed on ITT population and the same statistical testing as the primary analysis will be performed:

- Non-responder Imputation: any subjects without an evaluable vaccine response will be
  regarded as a Non-Responder. Non-evaluable vaccine response: defined as a response that
  cannot be classified as positive or negative due to missing assessment for the endpoint.
- **Observed Case**: No data will be imputed. All data as observed will be included in the analysis and the percentage will be calculated based on the number of observation available.
- COVID-19 Affected Case: Removal of subjects with COVID-19 (i.e. exclusion of subjects who
  had COVID-19).

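### Does the plan need a signed 10-point rule in the primary analysis section, and a different interval level for the secondary vaccine endpoints?

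*SAP*

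**What the plan says.** The margin is stated with the sample size. SAP 3.5 says about 245 subjects, 123 per arm, will be randomized "to show that the 90% confidence interval of the proportion difference between treatment groups will exclude a difference of more than 10" percent. Protocol 16.9 and the sample-size row of the synopsis say the same.

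The analysis text gives the estimator and interval without repeating the margin. SAP 8.1.1: "The analysis for primary endpoint will be using the Cochran-Mantel-Haenszel (CMH) estimate of the risk difference and corresponding 2-sided 90% CI". Protocol 16.4.2 agrees: "using the Cochran-Mantel-Haenszel (CMH) estimate of the risk difference and corresponding 2-sided 90% CI". The estimand table in SAP 3.1 names the same method. SAP 8.1.2 adds that for the sensitivity analyses "the same statistical testing as the primary analysis will be performed".

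On levels, SAP 6.1 states: "All statistical tests on the vaccine response endpoints will be conducted at the 2-sided 10% level and the 90% CI will be estimated". The general paragraph of Protocol 16 states, subject to a proviso for anything specified elsewhere, that "all statistical tests other than the primary vaccine response endpoint will be 2-sided and conducted at the 5% level", and then: "All presented confidence intervals will be 2-sided 95% confidence intervals". Protocol 16.4.4 and the synopsis both give the secondary vaccine endpoints the primary endpoint's methods. SAP 14.4, the entry on changes to the vaccine secondaries, mentions only added geometric mean ratios.

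**The concern.** Two things look wrong on a first reading.

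First, someone who opens only SAP 8.1.1 finds an estimate and an interval but no rule for a conclusion. SAP 6.1 and 8.1.2 speak of tests without naming a null hypothesis. The sizing sentence has no sign, so it could mean that nemolizumab must not lower response by more than 10 points (lower limit only), or that response must not differ by more than 10 points either way (both limits). Background text can be cited for each: Protocol 5.3.2 discusses possible interference with immunity, which is a loss, while Protocol 7.2 speaks of detecting any effect. If the rule were chosen after unblinding, it could be chosen to suit the result.

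Second, Protocol 16 exempts only the primary vaccine endpoint from 5% testing and calls for 95% intervals. SAP 6.1 applies 10% and 90% to every vaccine endpoint, and SAP 14 does not list this as a change. The meningococcal response belongs to the primary objective but is analysed only as a secondary endpoint, so the interval level could seem to matter for half of that objective.

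**Working it through.** **Inputs.** 123 per arm, 1:1 allocation, a two-sided 90% interval and a 10-point margin (Protocol 16.9, SAP 3.5). The visible text gives no response rate, power or dropout, so the rates p below are assumptions.

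**Can 123 per arm be reproduced?** Only with added assumptions. With no true difference and no dropout, n per arm = c × 2p(1−p) / 0.10².

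- Lower limit only, 80% power: c = (1.645 + 0.842)² ≈ 6.18. At p = 0.888, 6.18 × 2 × 0.888 × 0.112 / 0.01 ≈ 123.
- Both limits, 80% power: c = (1.645 + 1.282)² ≈ 8.56. At p = 0.922, 8.56 × 2 × 0.922 × 0.078 / 0.01 ≈ 123.

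Both readings fit at a plausible rate, so the sample size does not identify which was meant.

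**Is the planned interval right under both readings?** Yes. A two-sided 90% interval leaves 5% in each tail. Checking its lower limit against −10 points is a one-sided 5% test. Requiring both limits inside ±10 points is the usual pair of one-sided 5% tests. Neither reading needs a different estimator, level, population or data item.

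**How far apart are the readings?** Exact enumeration of all outcome pairs at 123 per arm, with an unstratified 90% Wald interval:

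| True response, placebo → nemolizumab (assumed) | Lower limit above −10 | Both limits within ±10 |
|---|---|---|
| 70% → 70% | 53% | 6% |
| 80% → 80% | 63% | 25% |
| 90% → 90% | 84% | 67% |
| 95% → 95% | 97% | 94% |
| 80% → 85% | 92.9% | 20.5% |
| 90% → 93% | 97.8% | 61% |
| 93% → 95% | 98.8% | 82% |
| 80% → 90% | 99.8% | 5.1% |

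The normal approximation agrees. At p = 0.80 the standard error is √(2 × 0.80 × 0.20 / 123) = 0.0510, and 0.10 / 0.0510 − 1.645 = 0.316. The lower-limit chance is therefore 62.4%, and the two-limit chance is 2 × 0.624 − 1 = 24.8%.

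For a true loss of 10 points from 90% to 80%, the pass rates are 5.4% and 5.1%. Both rules therefore guard against a loss at about the nominal 5%. They differ mainly in power and in how they treat a gain. How a gain fares under the two-limit rule depends on its size and the starting rate: 82% pass for 93 → 95, 5.1% for 80 → 90.

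**Interval level for the secondaries.** Half-width = z × √(2p(1−p)/123). At p = 0.80 this is 1.645 × 0.0510 = 8.4 points at 90% and 1.96 × 0.0510 = 10.0 points at 95%. At p = 0.90 it is 6.3 and 7.5 points.

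**Do the protocol passages conflict?** The 95% sentence in Protocol 16 cannot be literal, because Protocol 16.4.2 gives the primary a 90% interval. It is a default that yields to specific sections. The specific section for the vaccine secondaries is 16.4.4, which assigns them the primary's methods. The synopsis does the same directly after stating the primary's 90% interval. For the binary efficacy endpoints, which also follow the primary's manner, the protocol writes out 95%; for the vaccine secondaries it does not. SAP 6.1 can therefore be read as following 16.4.4, which would leave nothing for SAP 14 to list.

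**The case for a change.** The strongest case for a change is that the choice of limits can decide the result. Observed response of 93% on nemolizumab and 88% on placebo gives a difference of 5 points with standard error √((0.93 × 0.07 + 0.88 × 0.12)/123) = 0.0373, so a 90% interval of −1.1 to 11.1 points. That passes a lower-limit rule and fails a two-limit rule. The readings nearly agree only around 95% response, and Protocol 7.2 itself warns that subjects with high baseline titers may not reach a 4-fold rise. One sentence would close the matter at almost no cost.

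The arithmetic stands, and it is true that the margin is missing from the visible analysis sections. But the sentence would add no analysis. Either it writes down the natural reading of the sizing text, or it moves the trial to a loss-only rule, which has more power but ignores a gain. That choice belongs to the sponsor, and the documents do not show one answer to be wrong. With the margin prespecified and both limits reported, a later one-sided reading would be visible to anyone holding SAP 3.5. Nor does any passage say that a non-significant test will be taken as absence of effect.

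On the secondaries, it is fair that the efficacy text shows the primary's manner can go with a 95% interval, so the shared method alone does not prove 90%. What remains is an untidiness inside the protocol that SAP 6.1 settles openly.

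**Conclusion.** No change follows. The margin, interval level and estimator are all prespecified, though in different sections, and together they give an analyst what is needed: the stratified two-sided 90% interval, held against 10 points, with both limits inside as the plain reading of an unsigned difference. Repeating this in SAP 8.1.1 would be tidier but would alter no output. The gap between the readings is real (63% against 25% at 80% response, 84% against 67% at 90%, 123 per arm, no true effect), but it measures a trade-off between power and sensitivity to a gain.

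For the secondary vaccine endpoints, SAP 6.1 is consistent with Protocol 16.4.4 and the synopsis. Moving from 90% to 95% would widen the half-width from 8.4 to 10.0 points at 80% response. Since no margin is stated for these endpoints, no stated conclusion would change.

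This rests on assumed response rates, full evaluability at 123 per arm and an unstratified interval. The text after the endpoint list in SAP 8.2 and the code in SAP 20.1 are not visible, and either may already state the margin or level.
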